# **11. MEASUREMENT OF EFFECT**

# **11.1** Antitumor Effect

For the purposes of this study, patients should be re-evaluated for response every 12 weeks. In

addition to a baseline scan, confirmatory scans should also be obtained 12 weeks following initial documentation of objective response.

Response and progression will be evaluated in this study using criteria suggested by Tsukasaki et al [19].

# 11.1.1 Definitions

Evaluable for toxicity. All patients will be evaluable for toxicity from the time of their first treatment with nivolumab.

Evaluable for objective response. Only those patients who have measurable disease present at baseline, have received at least one cycle of therapy, and have had their disease re-evaluated will be considered evaluable for response. These patients will have their response classified according to the definitions stated below. (Note: Patients who exhibit objective disease progression prior to the end of cycle 1 will also be considered evaluable.)

Evaluable Non-Target Disease Response. Patients who have lesions present at baseline that are evaluable but do not meet the definitions of measurable disease, have received at least one cycle of therapy, and have had their disease re-evaluated will be considered evaluable for non-target disease. The response assessment is based on the presence, absence, or unequivocal progression of the lesions.

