## 4.4 General Guidelines

Following registration, patients should begin protocol treatment within 7 days. Issues that would cause treatment delays should be discussed with the Principal Investigator. If a patient does not receive protocol therapy following registration, the patient's registration on the study may be canceled. The Study Coordinator should be notified of cancellations as soon as possible.

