#### 13.2 Study Design

At least 20 evaluable patients will be enrolled for this study. Evaluable patients will be those patients who received study medication. The sample size of 20 patients is based on Simon's Optimal 2-stage design, with the assumption that an overall response rate of 40% is the minimum response rate that would be considered for further analysis of this approach, compared to a rate of 10% under null hypothesis. Thus, 20 subjects are required to with a one-side type 1 error rate of 5% and a power of 90%. If 1 or fewer responses are seen among the first 9 subjects enrolled, the trial is stopped early for futility. In contrast, if 2 or more responders are observed out of the 9 patients in the first stage, additional 11 patients will be enrolled in the 2nd stage. In a multicenter study such as this, however, it is difficult for a trial to reach the planned sample exactly. The investigators would not turn away patients who have already been approached for participation just because the number of patients needed has been met. Therefore, we adopted a flexible Phase II design (Chen and Ng 1998) to allow the actual number at final stage to deviate slightly from

what is planned. Due to the expected relatively low accrual rate, we expect that the interim analysis could be performed at the designed sample size. Only the decision boundaries at the 2nd-stage are determined following Chen and Ng's flexible design and programed by the study statistician [57]. That is, if 5 or more responders are observed out of 20-23 patients, or 6 or more responders are observed out of 24-25 patients, we would conclude that preliminary evidence for efficacy exists and that further investigation of the treatment is warranted.

The interim analysis will be based upon independent review of response, with a minimum time frame of 2 months for the interim analysis. Accrual will not be halted during the interim analysis.

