#### **13.4.2** Evaluation of Response

All patients included in the study must be assessed for response to treatment, even if there are major protocol treatment deviations or if they are ineligible. Each patient will be assigned one of the following categories: 1) complete response, 2) partial response, 3) stable disease, 4) progressive disease, 5) early death from malignant disease, 6) early death from toxicity, 7) early death because of other cause, or 8) unknown (not assessable, insufficient data). [Note: By arbitrary convention, category 8 usually designates the "unknown" status of any type of data in a clinical database.]

All of the patients who met the eligibility criteria (with the possible exception of those who received no study medication) should be included in the main analysis of the response rate. Patients in response categories 4-9 should be considered to have a treatment failure (disease progression). Thus, an incorrect treatment schedule or drug administration does not result in exclusion from the analysis of the response rate. Precise definitions for categories 4-9 will be protocol specific.

All conclusions should be based on all eligible patients. Subgroup analyses may then be performed on the basis of a subset of patients, excluding those for whom major protocol deviations have been identified (*e.g.*, early death due to other reasons, early discontinuation of treatment, major protocol violations, etc.). However, these subgroup analyses may not serve as the basis for drawing conclusions concerning treatment efficacy, and the reasons for excluding patients from the analysis should be clearly reported. The 95% confidence intervals should also be provided.

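### Sections 11.1.1, 13.2 and 13.4.2 define three different populations for the primary response rate; 13.4.2 is the best reading, but nothing ranks them

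*Combined protocol and SAP*

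**What the plan says.** The primary efficacy endpoint is the overall response rate, CR plus PR (13.1). Three sections say who is counted.

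- **11.1.1 Definitions.** Evaluable for objective response are "Only those patients who have measurable disease present at baseline, have received at least one cycle of therapy, and have had their disease re-evaluated". A note adds patients with objective progression before the end of cycle 1. A separate category covers patients whose lesions are evaluable but not measurable; they are judged on whether lesions are present, absent or unequivocally progressing.
- **13.2 Study Design.** "Evaluable patients will be those patients who received study medication". There is no condition on eligibility, measurability or re-evaluation. The plan is to enrol at least 20 evaluable patients. The trial stops for futility "If 1 or fewer responses are seen among the first 9 subjects enrolled". Efficacy is concluded "if 5 or more responders are observed out of 20-23 patients", or with 6 or more of 24 or 25.
- **13.4.2 Evaluation of Response.** Patients who met the eligibility criteria, possibly without the untreated, "should be included in the main analysis of the response rate". Early deaths and unknown responses count as failures. "All conclusions should be based on all eligible patients". Analyses that leave out patients with major deviations "may not serve as the basis for drawing conclusions concerning treatment efficacy".

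Three other places bear on this. Section 3.1 admits all four ATLL subtypes and does not require measurable disease. The table in 11.1.4 scores skin and peripheral blood, with partial remission at a decrease of at least 50%. Section 4.4 says that an untreated patient's "registration on the study may be canceled".

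**The concern.** The word evaluable carries two meanings, and the sample size and decision rule are written in terms of it. No sentence says which definition governs the primary analysis or that the 11.1.1 set is supportive.

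The sets differ in ways that matter in this disease. Formal re-evaluation comes every 12 weeks (11.1), and median survival in the acute and lymphomatous forms is 3 to 6 months (2.1.1). Some treated patients may therefore leave before any re-evaluation and without documented progression. Section 13.4.2 counts them as failures; 11.1.1 removes them. Patients with blood-only disease, or with small or non-measurable skin disease, can enrol and can be scored under 11.1.4, yet 11.1.1 puts them outside the objective-response set.

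With 20 to 25 patients and a rule that turns on one responder, the choice of set affects the reported rate and, in some readings, the conclusion and the error rates.

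**Working it through.** **1. The plan's own design.** Inputs from 13.2: null rate 10%, target rate 40%, 9 patients in stage 1 (continue with 2 or more responses), 20 in total (success with 5 or more).

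P(success | p) = sum over x = 2 to 9 of P(X1 = x; n = 9, p) × P(X2 ≥ 5 − x; n = 11, p)

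- p = 0.10: 0.0349, within the stated 5%.
- p = 0.40: 0.9018, matching the stated 90%.

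The design reproduces, so the question is only which patients the 9 and the 20 are.

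**2. The definitions side by side.**

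| Patient | 11.1.1 | 13.2 | 13.4.2 |
|---|---|---|---|
| Treated, eligible, measurable, re-evaluated | in | in | in |
| Treated, eligible, never re-evaluated, no documented early progression | out | in | in, as failure |
| Treated, eligible, no measurable lesion | separate category | in | in |
| Treated, later found ineligible | not addressed | in | outside the set for conclusions |
| Eligible, never treated | out | out | possibly out |

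**3. Effect of 11.1.1 on the estimate.** The number of unassessed patients is an assumption. Exact (Clopper-Pearson) 90% intervals:

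- 4 responders of 20 treated: 20.0% (7.1% to 40.1%).
- The same 4 after dropping 4 unassessed non-responders: 4/16 = 25.0% (9.0% to 48.4%).

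Four responders are below every boundary, and 13.2 gives no boundary below 20 patients. This example changes the estimate, not the decision. Moving out patients without measurable lesions could raise or lower the rate, so the net direction is unknown.

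**4. Effect on type I error if enrolment runs to 20 patients evaluable under 11.1.1.** Let q be the share of treated patients who are non-evaluable non-responders; the documents give no value. If the response rate among all treated is 10%, the rate among the evaluable is 0.10/(1 − q). Putting that rate into the formula in step 1:

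| q | Rate among evaluable | P(success) |
|---|---|---|
| 0 | 10.0% | 3.5% |
| 10% | 11.1% | 5.1% |
| 15% | 11.8% | 6.3% |
| 20% | 12.5% | 7.8% |

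**5. 13.2 against 13.4.2.** Suppose 5 of 20 treated patients respond: 25.0% (90% CI 10.4% to 45.6%), which meets the boundary. If one of the five is later found ineligible, 13.4.2 gives 4/19 = 21.1% (7.5% to 41.9%). That does not meet it, and no boundary is stated for 19.

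**6. The stage-1 wording.** Read literally, enrolled could include untreated patients whose registration was not cancelled. If 1 or 2 of the first 9 were such patients, P(1 or fewer responses) at a 40% rate would be 10.6% or 15.9% instead of 7.1%. Power with 20 treated in total would be 87.0% or 82.2% instead of 90.2%. This takes enrolled literally at stage 1 and treated at the end, so it is a bound on a wording slip and not a forecast.

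**The case against.** The strongest answer is that 13.4.2 already settles the matter. It alone speaks of the main analysis and of all conclusions, it keeps early deaths and unknowns in the denominator, and it bars subset analyses as a basis for efficacy claims. That largely stands, and it is why this is a point of reconciliation. It does not close the gap, because the bar is illustrated by deviations, early deaths and early discontinuation. Lack of measurable disease is not a deviation, and the 11.1.1 set is not named.

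A second answer is that 11.1.1 does provide for patients without measurable lesions. It does, but on a scale that cannot express the 50% decrease in skin or blood that 11.1.4 accepts as partial remission, and nothing says that the category feeds the response rate.

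Third, treated-but-ineligible patients should be rare, since 4.3 requires central review of eligibility documents before registration and 4.3.2 requires a site check. Untreated patients among the first 9 should also be rare, since 4.4 expects treatment within 7 days and allows cancellation, and 13.2 itself defines evaluable as treated. Both answers stand; these two conflicts are minor.

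A reader might infer that the trial's type I error exceeds 5%, or that the response rate will be overstated. The documents support neither. The error stays at 3.5% for 20 patients when 13.2's treated definition governs. The higher figures need the 11.1.1 meaning, enrolment continued to 20 such patients, and assumed values of q.

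**Conclusion.** The conflict is real and should be fixed before analysis. Section 13.4.2 is the best reading of the main analysis, but 11.1.1 states a different rule in exclusive terms, is not marked supportive, and shares its key word with 13.2.

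If 11.1.1 were followed, the illustrated shift is from 20% to 25% with four unassessed patients in 20. If it also governed enrolment, type I error would be 5.1% to 7.8% for q between 10% and 20%. The disagreement between 13.2 and 13.4.2 over ineligible patients can reverse the conclusion, but only when the result sits on the boundary. All counts of affected patients are assumptions. The 9 + 11 design and its boundaries are not in question.

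**What to change.** - **13.2:** state that one denominator governs the response rate and the decision rule at both stages, namely patients who received at least one dose of nivolumab. State the stage-1 rule on the first 9 treated patients.
- **13.4.2:** align the eligibility wording with that set. Keep its rule that patients with no post-baseline response assessment (early death or unknown) are non-responders. Say that a patient who met the response criteria before stopping treatment remains a responder: 13.4.2 does not make discontinuation a failure, and 11.1.4.1 records best response until progression. Correct the reference to categories 4 to 9, since only eight are listed.
- **11.1.1:** label the set supportive, refer to 13.4.2, and state that patients without measurable lesions stay in the response rate and are scored by the 11.1.4 criteria.

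The cost is wording in three sections, with no change to sample size or boundaries. If 13.4.2 is already being followed, the denominator changes only through treated patients later found ineligible, and through any eligible but untreated patients whom 13.4.2 leaves optional.

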# **11.1.2 Disease Parameters**

Measurable disease. Measurable lesions are defined as those that can be accurately measured in at least one dimension (longest diameter to be recorded) as  $\geq 20 \text{ mm}$  ( $\geq 2 \text{ cm}$ ) by chest x-ray or as  $\geq 10 \text{ mm}$  ( $\geq 1 \text{ cm}$ ) with CT scan, MRI, or calipers by clinical exam. All tumor measurements must be recorded in millimeters (or decimal fractions of centimeters).

Note: Tumor lesions that are situated in a previously irradiated area might or might not be considered measurable.

Malignant lymph nodes. To be considered pathologically enlarged and measurable, a lymph node must be  $\geq 15 \text{ mm}$  ( $\geq 1.5 \text{ cm}$ ) in short axis when assessed by CT scan (CT scan slice thickness recommended to be no greater than 5 mm [0.5 cm]). At baseline and in follow-up, only the short axis will be measured and followed.

Non-measurable disease. All other lesions (or sites of disease), including small lesions (longest diameter <10 mm [<1 cm] or pathological lymph nodes with  $\ge10$  to <15 mm [ $\ge1$  to <1.5 cm] short axis), are considered non-measurable disease. Bone lesions, leptomeningeal disease, ascites, pleural/pericardial effusions, lymphangitis cutis/pulmonitis, inflammatory breast disease, and abdominal masses (not followed by CT or MRI), are considered as non-measurable.

Note: Cystic lesions that meet the criteria for radiographically defined simple cysts should not be considered as malignant lesions (neither measurable nor non-measurable) since they are, by definition, simple cysts.

'Cystic lesions' thought to represent cystic metastases can be considered as measurable lesions, if they meet the definition of measurability described above. However, if non-cystic lesions are present in the same patient, these are preferred for selection as target lesions.

Target lesions. All measurable lesions up to a maximum of 2 lesions per organ and 5 lesions in total, representative of all involved organs, should be identified as **target lesions** and recorded and measured at baseline. Target lesions should be selected on the basis of their size (lesions with the longest diameter), be representative of all involved organs, but in addition should be those that lend themselves to reproducible repeated measurements. It may be the case that, on occasion, the largest lesion does not lend itself to reproducible measurement in which circumstance the next largest lesion which can be measured reproducibly should be selected. A sum of the diameters (longest for non-nodal lesions, short axis for nodal lesions) for all target lesions will be calculated and reported as the baseline sum diameters. If lymph nodes are to be included in the sum, then only the short axis is added into the sum. The baseline sum diameters will be used as reference to further characterize any objective tumor regression in the measurable dimension of the disease.

Non-target lesions. All other lesions (or sites of disease) including any measurable lesions over and above the 5 target lesions should be identified as **non-target lesions** and should also be recorded at baseline. Measurements of these lesions are not required, but the presence, absence, or in rare cases unequivocal progression of each should be noted throughout follow-up.

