# **11.1.3 Methods for Evaluation of Measurable Disease**

All measurements should be taken and recorded in metric notation using a ruler or calipers. All baseline evaluations should be performed as closely as possible to the beginning of treatment and never more than 4 weeks before the beginning of the treatment.

The same method of assessment and the same technique should be used to characterize each identified and reported lesion at baseline and during follow-up. Imaging-based evaluation is preferred to evaluation by clinical examination unless the lesion(s) being followed cannot be imaged but are assessable by clinical exam.

Clinical lesions will only be considered measurable when they are superficial (*e.g.*, skin nodules and palpable lymph nodes) and  $\geq 10 \text{ mm}$  ( $\geq 1 \text{ cm}$ ) diameter as assessed using calipers (*e.g.*, skin nodules). In the case of skin lesions, documentation by color photography, including a ruler to estimate the size of the lesion, is recommended.

All subjects with skin disease and/or erythema using the SWAT and will have photographs taken using a digital camera. Special care should be taken to shield the patient's identity

Photos must be provided labeled with patient's protocol number and initials and date.

The body is divided into 12 regions with preassigned percentage total body surface area (%TBSA) based on methodology used to assess burns: head is 7% BSA, neck 2%, ant trunk 13%, post trunk 13%, buttocks 5%, genitals 1%, upper arms 8%, forearms 6%, hands 5%, thighs 19%, lower leg 14%, feet 7%.

Biopsies at baselines and subsequent times can be performed to confirm a CR at the discretion of the investigator.

Chest x-ray: Lesions on chest x-ray are acceptable as measurable lesions when they are clearly defined and surrounded by aerated lung. However, CT is preferable.

Conventional CT and MRI: This guideline has defined measurability of lesions on CT scan based on the assumption that CT slice thickness is 5 mm (0.5 cm) or less. If CT scans have slice thickness greater than 5 mm (0.5 cm), the minimum size for a measurable lesion should be twice the slice thickness. MRI is also acceptable in certain situations (*e.g.* for body scans).

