# 11.1.4 Response Criteria

Response Criteria for Adult T-Cell Leukemia-Lymphoma									
Response	Definition	Lymph Nodes	Extranodal Masses	Spleen, Liver	Skin	Peripheral Blood	Bone Marrow		
Complete Remission 	Disappearance of all disease	Normal	Normal	Normal	Normal	Normal 	Normal		
Uncertified Complete Remission 	Stable residual mass in bulky lesion	$\geq 75\%$ decrease 	$\frac{>75\%}{\text{decrease}^3}$	No increase	≥50% decrease	$\geq 50\%$ decrease	Normal		
Partial Remission 	Regression of disease	$\geq 50\%$ decrease 	$\geq 50\%$ decrease 	No increase	$\geq 50\%$ decrease	$\geq 50\%$ decrease	Irrelevant		
Stable Disease 	Failure to attain complete/partial remission and no progressive disease	No change in size	No change in size	No change in size	No chance in size	No change	No change		
Relapse Disease or Progressive Disease	New or increased lesions	New or $\geq 50\%$ increase 	New or $\geq 50\%$ increase 	New or $\geq 50\%$ increase	New or $\geq 50\%$ increase	New or $\geq 50\%$ increase 	Re- appearance		
Not Assessable									

Require each criterion to be present for a period of at least 4 weeks

 Provided that <5% of flower cells remained, complete remission was judged to have been attained if the absolute lymphocyte count, including flower cells, was  $<4x10^{9}/L$ 

Calculate by the sum of the products of the greatest diameters of measurable disease

 Defined by  $\geq$  50% increase from nadir in the sum of the products of measurable disease

 Defined by  $\geq$ 50% increase from nadir in the count of flower cells and an absolute lymphocyte count, including flower cells, of >4x10^9/L

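### Section 11.1.2 records single diameters, but the Section 11.1.4 response table and irRC both need sums of products, and the statements on which criteria govern contradict each other

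*Combined protocol and SAP*

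**What the plan says.** **Measurement rules (Section 11.1.2).** "Measurable lesions are defined as those that can be accurately measured in at least one dimension". For malignant nodes, "At baseline and in follow-up, only the short axis will be measured and followed". Target lesions are capped at 2 per organ and 5 in total. Their burden is a single-diameter sum: "A sum of the diameters (longest for non-nodal lesions, short axis for nodal lesions) for all target lesions will be calculated". Its purpose is then given: "The baseline sum diameters will be used as reference to further characterize any objective tumor regression in the measurable dimension of the disease". Measurable lesions beyond the targets become non-target lesions, and "Measurements of these lesions are not required".

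**Response table (Section 11.1.4).** For nodes and extranodal masses, uncertified complete remission and partial remission need decreases of 75% and 50%. Footnote 3 gives the metric: "Calculate by the sum of the products of the greatest diameters of measurable disease". Footnote 4 sets progression at a 50% rise from nadir, again on products.

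**irRC (Appendix D).** Measurable lesions need two perpendicular diameters. The metric is a sum of products on up to 5 lesions per organ and 10 in total. Partial response is a 50% fall and progression a 25% rise.

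**Which criteria govern.** Section 11.1: "Response and progression will be evaluated in this study using criteria suggested by" the ATLL consensus proposal (reference 19), which Section 11.1.4 tabulates. Section 13.3 adds the irRC response rate as a further estimate. Appendix C (Image Acquisition Guidelines) and Appendix D (lesion definitions) instead have the investigator base response on irRC. Appendix D's text on the nadir sum makes irRC the basis of key efficacy endpoints.

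**The concern.** The primary efficacy endpoint in Section 13.1 is the CR+PR rate. When a patient's category depends on node or mass size, the table needs a sum of products. A short axis for nodes, or a longest diameter for other masses, does not determine a product. irRC is product-based too, so Section 11.1.2 falls short whichever criteria govern.

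Appendix D's two-diameter instruction also conflicts directly with the short-axis-only sentence for nodes, so a site cannot comply with both as written. The two sets of criteria differ in lesion caps and progression thresholds as well. Two readers could therefore each follow part of the protocol and classify the same patient differently. Best overall response is counted until progression (Section 11.1.4.1), so the progression rule can matter as well as the response rule.

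**Working it through.** **The plan's own figures.** This point disputes no stated number. The design in Section 13.2 (null rate 10%, target 40%, one-sided 5%, power 90%) reproduces: stop at 1 or fewer responses in 9, positive at 5 or more in 20, exact type I error 0.0349, power 0.9018. It only sets the scale: one patient is 1/20 = 5 percentage points of response rate.

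**Assumptions for the examples.** The node sizes are illustrative and not from the documents. One node is the only disease deciding the category, there are no new lesions, and the finding lasts the required 4 weeks. Baseline (or nadir) is 30 x 20 mm, product 30 x 20 = 600.

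**1. Regression.** Change in product = (long x short)/600 - 1. Short axis falls from 20 to 13 mm (-35%).

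| Long axis (mm) | Product | Change | At the 50% cut-off |
|---|---|---|---|
| 30 | 390 | -35.0% | not partial response |
| 23 | 299 | -50.2% | partial response |
| 13 | 169 | -71.8% | partial response |

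Section 11.1.2 records 20 and 13 mm in every row. The 50% cut-off is the same in Section 11.1.4 and irRC, so both are affected. For a fractional short-axis fall s, the long-axis fall needed for partial response is 1 - 0.5/(1 - s):
- s = 0.35: 1 - 0.5/0.65 = 23.1%
- s = 0.40: 1 - 0.5/0.60 = 16.7%

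A second pair shows the same: 21 x 14 = 294 (-51.0%) and 30 x 14 = 420 (-30.0%) share one short axis. The information is missing, not merely on another scale.

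**2. Growth from nadir.** Short axis rises from 20 to 24 mm (+20%).

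| Long axis (mm) | Product | Change | irRC (25%) | Section 11.1.4 (50%) |
|---|---|---|---|---|
| 30 | 720 | +20% | no | no |
| 36 | 864 | +44% | progression | no |
| 37.5 | 900 | +50% | progression | progression |

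Section 11.1.2 records 20 and 24 mm each time. The long-axis growth needed is 1.25/1.2 - 1 = 4.2% for irRC and 1.5/1.2 - 1 = 25% for Section 11.1.4.

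**3. Lesion set.** Take 8 lesions, measurable under both definitions, 4 in each of two organs.
- Section 11.1.2: min(5, 2 + 2) = 4
- Appendix D: min(10, 4 + 4) = 8
- Footnote 3 states no cap: 8 read literally, or 4 if Section 11.1.2 is meant to supply the set

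**The case against.** **The second diameter is often collected anyway.** Appendix D requires a sum of products at every on-study assessment, on a larger lesion allowance, and has investigators supply the measurements. A site following the whole protocol would usually hold both diameters. This stands, and the data gap is partial. A reader might infer that response cannot be determined at all, and the documents do not support that. What is left is that Appendix D contradicts the short-axis-only sentence, uses another lesion set, and is nowhere linked to Section 11.1.4.

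**Images can be re-read.** Appendix C keeps imaging data, Section 11.1.7 provides independent review, and Section 13.2 bases the interim analysis on it. This also stands, with one exception. Clinically assessed lesions "will only be considered measurable when they are superficial" and at least 10 mm by calipers, so a palpable node followed only that way leaves no image to re-measure. The exception is narrow: Section 11.1.3 prefers imaging, and Appendix C asks for chest, abdomen and pelvis scans at each assessment. It is not empty, because the Schema limits 12-weekly imaging to patients with abnormal imaging. Nor is the independent reviewer told which metric or lesion set to apply.

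**The diameter sum may be only descriptive.** Section 11.1.2 uses it to characterise regression further, and the table has no threshold on it. A reader might infer a rival response criterion, and the wording does not go that far. The obstacle is what gets measured.

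**Precedence is stated.** A reader might infer that the protocol is silent on which criteria govern. It is not: it speaks in incompatible ways, which still needs correcting.

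**The examples are chosen to straddle cut-offs.** True. They show that a category can be undetermined, not how often. Two sets of criteria may also legitimately have different progression thresholds; that alone is no fault in Section 11.1.2.

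**Conclusion.** The point holds as a conflict between measurement rules, combined with contradictory statements about which criteria govern. Confidence in the conflict is high, because it rests on current text. One short-axis reading is compatible with partial response and with none, under Section 11.1.4 and under irRC.

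The effect on the response rate cannot be sized. It is confined to patients whose category depends on node or mass size; spleen and liver, skin, blood and marrow have their own columns in the table. The documents do not say how many such patients there will be. The figure of 5 percentage points per patient at n = 20 is scale, not likelihood. A reader might infer that the response rate will be biased, or the design's error rates altered. Nothing in the documents gives a direction or an amount, so neither is claimed.

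It should be fixed: it touches the primary endpoint and the correction is cheap.

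**What to change.** 1. In Section 11.1.2, replace the short-axis-only instruction with recording both perpendicular diameters of every target lesion, nodes included, at baseline and each assessment, by imaging or calipers. Make the sum of products the baseline and nadir reference for the Section 11.1.4 table. Leave the definition of measurable disease unchanged, because Section 11.1.1 ties evaluability for response to it.
2. State that the Section 11.1.4 criteria define the primary CR+PR endpoint and that irRC is the additional analysis in Section 13.3. Amend the endpoint wording in Appendix C (Image Acquisition Guidelines) and Appendix D (lesion definitions and nadir sum) to match.
3. Say which lesion set footnotes 3 and 4 use, and have the independent reviewer apply the same rule.
4. Section 5.8 relies on a total single diameter relative to baseline. It must be reconciled with Section 11.1.2; keep the single-diameter sum recorded until that is done.

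**Cost.** Protocol wording and one more measurement per target lesion on the same images or examination, with more if a larger lesion set is chosen. No extra scans are needed. The case report forms are not in the documents, so a new field may or may not be required.
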